STUDY PROTOCOL AND STATISTICAL ANALYSIS PLAN

Official title: Problem-Solving Training for Care Partners of Adults with Traumatic Brain Injury

NCT number: NCT03739450

IRB approved date: 06-02-20

**The University of Texas Southwestern Medical Center at Dallas
Institutional Review Board**

Protocol Template (for Investigator Initiated Studies)

Title: Problem-Solving Training for Care Partners of Adults with Traumatic Brain Injury

1. Introduction and Purpose: The purpose of this project is to:

AIM 1: Assess the feasibility of delivering up to 6 sessions of Problem Solving Training (PST) to care partners of individuals with traumatic brain injuries (TBI) during the inpatient rehabilitation stay.

- **Hypothesis 1a:** Care partners will complete at least three intervention sessions (in person and/or via telephone) prior to discharge from inpatient rehabilitation and will report high satisfaction.
- **Aim1a:** Determine the number of sessions that it is feasible to complete during the inpatient rehabilitation stay and factors associated with non-compliance.

AIM 2: Assess the efficacy of PST plus TBI-specific education compared to TBI-specific education alone for improving the outcomes of care partners of individuals with TBI.

- **Hypothesis 2a:** PST will reduce care partners' burden and depressive symptoms (primary), while improving care partners' coping skills (secondary) at one-month post discharge more than TBI-specific education alone.
- **Hypothesis 2b:** Effects of the PST intervention on care partner burden, depressive symptoms, and coping will be maintained at 6 months post-intervention.

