2. Background: The chronic consequences of TBI are recognized, but ongoing support for adults with TBI living in the community is limited. This puts undue burden on care partners, particularly during the transition from hospital to home. It often leads to adverse consequences among care partners, such as emotional distress and increased substance abuse.^{1,2} Care partners of individuals with TBI often experience high levels of burden, which may result in depression, anxiety, increased somatic symptoms, and reduced quality of life.^{1,3,4} Care partner burden is largely predicted by the extent to which care partners' perceived needs are met.^{1,5,6} As the consequences of TBI continue to change over time, so too do the perceived needs of care partners.⁷⁻¹¹ One study suggests that only 55% of care partner needs are perceived as being met.¹² A systematic review of qualitative studies for care partners of adults with stroke revealed seven themes with regard to experiences, needs, and preferences of care partners during inpatient rehabilitation.¹³ Care partners expressed a desire to be included, informed, and recognized as a stakeholder in recovery, the need to navigate an alien culture and environment, and the need to manage the transition home.¹³ The authors concluded that "we need to make deliberate efforts to provide a more inclusive environment that better supports and prepares carers for their new role".¹³ Despite this established need during inpatient rehabilitation, there are currently no evidence-based interventions for care partners of adults with TBI to prepare them for their new role prior to discharge of care recipients from inpatient rehabilitation. Hence, there is a critical need to provide care partners of individuals with TBI with the necessary skills to navigate this difficult transition from hospital to home.¹⁴ Self-management training for care partners of adults with other chronic conditions demonstrates strong potential for application to care partners of adults with TBI.

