3. Concise Summary of Project: Participants are care partners of adults with TBI who are inpatient patients at Zale Lipshy Hospital or Parkland Memorial Hospital. They will complete baseline testing and follow-up testing at 1-month and 6-months post-intervention. They will participate in up to 6 sessions of the Problem Solving Training intervention, delivered in person or via telephone. These data will be used to assess the feasibility of delivering this intervention. These data will also be used for secondary analysis to determine relationships between baseline measures, demographics, and outcomes among care partners of adults with traumatic brain injuries.

4. Study Procedures: This will be a randomized controlled trial, with blocked randomization stratified by performance site, of PST + Education vs Education alone for care partners of adults with TBI admitted to inpatient rehabilitation. Baseline assessment and all intervention sessions will occur during the time the patient with TBI is in inpatient rehabilitation, with the exception of the last intervention session, which can occur via telephone post-discharge. Follow-up assessments will occur at 1-month and 6-months after the completion of the intervention.

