14. Biostatistics: Specific Aim 1: The primary outcome is the total number of sessions completed prior to discharge, with a threshold of 80% of participants completing a minimum of 3 sessions as an indicator of feasibility. We will descriptively present reasons for non-compliance and explore factors associated with non-compliance (e.g. demographics, hospital length of stay, etc.). The secondary outcome for feasibility is satisfaction, with an item mean of ≥ 3.5 on the CSQ-8 as an indicator of high satisfaction. **Specific Aim 2:** To test our first hypothesis, we will use intent-to-treat analyses to measure the pre-post-test differences in each outcome between baseline and 1-month follow-up using a paired t-test or Wilcoxon signed rank test as appropriate. To address our second hypothesis, we will use intent-to-treat analyses to measure the pre-post-test differences in each outcome between baseline and 6-month follow-up (all participants) using paired t-tests or Wilcoxon signed rank tests. Effect sizes will be calculated and interpreted as follows: <0.2 =no/minimal effect; $0.2-0.5$ = small effect; $0.5-0.8$ =medium effect; ≥ 0.8 =large effect.

References

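### The effect-size bands are tied to paired pre-post tests, with no defined statistic and no interval, so the labels do not describe PST + Education versus Education

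*Combined protocol and SAP*

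**What the plan says.** Section 1 (Introduction and Purpose) sets Aim 2 as a comparison of arms: "Assess the efficacy of PST plus TBI-specific education compared to TBI-specific education alone". Hypothesis 2a expects PST to lower burden and depressive symptoms, and ends "while improving care partners' coping skills (secondary) at one-month post discharge more than TBI-specific education alone". Section 4 (Study Procedures) gives the matching design: "This will be a randomized controlled trial, with blocked randomization stratified by performance site, of PST + Education vs Education alone".

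Section 14 then specifies the Aim 2 analysis. Change from baseline to 1 month is examined "using a paired t-test or Wilcoxon signed rank test as appropriate". The 6-month analysis covers the difference between "baseline and 6-month follow-up (all participants) using paired t-tests or Wilcoxon signed rank tests". The interpretive rule follows directly: "Effect sizes will be calculated and interpreted as follows: <0.2 =no/minimal effect". The remaining bands are 0.2-0.5 small, 0.5-0.8 medium and 0.8 or more large.

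The section does not state:
- which effect-size statistic is meant, or which SD divides it;
- whether it is computed within an arm, across all participants or between arms;
- how it is obtained when the Wilcoxon test is used;
- whether the bands apply to the signed or the absolute value;
- whether a confidence interval accompanies it.

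A value of exactly 0.5 falls in two bands.

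**The concern.** The bands are the only stated thresholds for reading the Aim 2 results. Aim 1 has explicit criteria (80% of participants completing at least 3 sessions; a CSQ-8 item mean of at least 3.5). Aim 2 has tests, but no stated alpha, target effect or success criterion.

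Three things are at stake. First, the only analyses to which the bands are attached measure change within people, so the effect size can miss the randomised comparison altogether. Second, because the statistic is undefined, the same data can carry different labels depending on a choice made after they are seen. Third, the lowest band turns a point estimate into a negative conclusion without regard to its precision.

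**Working it through.** The plan states no effect size, sample size, SD or correlation, so there is no figure to reproduce. The steps below apply the rule as written over assumed values.

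**Inputs.** From Section 14: the cut-points 0.2, 0.5 and 0.8, and the paired tests. Assumed: equal SDs at both visits, pre-post correlation r of 0.2, 0.5 or 0.8, 20 to 100 pairs, and 20, 40 or 80 per arm.

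**Step 1: within-person change against arm difference.** Let both arms improve by 0.6 SD of the scores. At r = 0.5 the paired effect is 0.6 (*medium*) in each arm, while the arm difference is 0.6 - 0.6 = 0. Conversely, if the PST + Education arm does not change and the Education arm worsens by 0.5 SD, the paired effect in the PST + Education arm is 0 (*no/minimal*), although the arms differ by 0.5 SD in favour of PST.

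**Step 2: dependence on r.** Let d be the mean change divided by the SD of the scores, and dz the mean change divided by the SD of the change. With equal SDs, dz = d / sqrt(2(1 - r)). The d needed to reach a cut-point c on the dz scale is therefore c × sqrt(2(1 - r)).

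| r | sqrt(2(1 - r)) | d labelled *medium* from | d labelled *large* from |
|---|---|---|---|
| 0.2 | 1.265 | 0.63 | 1.01 |
| 0.5 | 1.000 | 0.50 | 0.80 |
| 0.8 | 0.632 | 0.32 | 0.51 |

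At r = 0.5 the two scales agree. At r = 0.8 a change of 0.32 SD, which is *small* on the score scale, is *medium* on the dz scale.

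**Step 3: precision of a paired estimate below 0.2.** SE(dz) is about sqrt(1/n + dz²/(2n)). For an observed dz of 0.15:
- n = 20 pairs: SE = sqrt(0.0500 + 0.0006) = 0.225, 95% CI -0.29 to 0.59.
- n = 40 pairs: SE = sqrt(0.0250 + 0.0003) = 0.159, 95% CI -0.16 to 0.46.
- n = 100 pairs: SE = sqrt(0.0100 + 0.0001) = 0.101, 95% CI -0.05 to 0.35.

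All three would be labelled *no/minimal*. Each interval extends well into *small*, and at 20 pairs into *medium*.

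**Step 4: precision of a between-arm estimate near zero.** SE(d) is about sqrt(2/n) with n per arm. The 95% half-width, 1.96 × sqrt(2/n), is 0.62, 0.44 and 0.31 at 20, 40 and 80 per arm. For an estimate of exactly 0 to have its whole interval within ±0.2, n must be at least 2 × (1.96/0.2)² = 192.1, so 193 per arm. Adjusting for baseline multiplies the variance by about 1 - r², which gives 185, 145 and 70 per arm at r = 0.2, 0.5 and 0.8.

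**The case against.** The best defence is that Section 14 names no statistic. The analyst could use one standardised mean change throughout, whichever test supplies the p-value, and could even compute it between arms. The hypotheses are addressed by the tests, the bands are verbal descriptors, and no success or stopping rule hangs on them. Most of this stands and it limits the weight of the point. It does not remove it: the only analyses to which the bands are attached are paired, and nothing tells the analyst to depart from them.

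Two stronger readings are tempting, and the documents do not support either.

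One is that the plan applies a single set of bands to statistics on different scales. If the analyst took Z/sqrt(n) after a Wilcoxon test, a paired effect of 0.5 would give about 0.45 (*small*) and 0.8 about 0.64 (*medium*), with a ceiling near 0.87. Section 14 does not say that this statistic will be used. With the matched rank-biserial instead, 0.5 gives about 0.52, still *medium*. Mixed scales are possible but are not stated.

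The other is that every worsening would be labelled *no/minimal*, because negative values lie below 0.2. That requires banding the signed value and coding every outcome so that positive means benefit, and neither is stated. Such bands are ordinarily read by magnitude. On a signed follow-up-minus-baseline reading, improvement in burden and depressive symptoms would be hidden instead. Nor does Section 2 (Background) predict worsening in this trial. Its remark, "This puts undue burden on care partners, particularly during the transition from hospital to home", is general context, and Hypothesis 2a predicts a reduction.

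**Conclusion.** The point holds as a defect of definition and target. Followed as written, the Aim 2 effect sizes describe within-person change and not PST + Education versus Education. Their labels are not reproducible, because the statistic, standardiser and sign are left open. An imprecise estimate below 0.2 can be read as *no/minimal effect*.

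The dependence on the pre-post correlation arises only if the effect size is mean change over the SD of change, and it vanishes at r = 0.5. At r = 0.8 the entry to *medium* falls from 0.50 to 0.32 score SDs, and at r = 0.2 it rises to 0.63. All sample sizes and correlations here are assumptions. No decision rule depends on the labels, so the damage is to interpretation. The change is still worth making because it lets the effect size answer the question Aim 2 asks.

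**What to change.** Replace the effect-size sentence in Section 14 with text to this effect:

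> For every outcome and visit, whichever test gives the p-value, one between-arm effect size is reported: the baseline-adjusted PST + Education minus Education difference in the follow-up score, divided by the pooled within-arm SD of the scores, signed so that positive favours PST, with its 95% CI. The bands apply to the absolute value (<0.2 no/minimal; 0.2 to <0.5 small; 0.5 to <0.8 medium; ≥0.8 large), and the direction is always stated. Where the estimate is below 0.2 in absolute value but the CI extends beyond -0.2 to 0.2, the result is described as imprecise and not as no effect.

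The last sentence is confined to estimates below 0.2, so a clear effect is never called inconclusive. The plan should also say at which visit the SD is taken. If within-arm change is shown as well, it should be divided by the SD of the scores so that it does not move with r.

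The cost is one paragraph, and no new data are needed because baseline is already collected. The main downside is that with modest samples *no/minimal effect* could not be concluded: this needs about 193 per arm without credit for baseline adjustment, and 185 to 70 per arm with it for r from 0.2 to 0.8. A mean-over-SD measure is also less apt for strongly skewed scores, where a rank-based measure can be shown beside it without band labels. This change corrects the effect size only. The paired tests have the same within-person limitation and need their own correction.
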